### *Eligibility Criteria*

1. Patients must be at least 18 years.
2. Able to provide consent for study participation (English and Spanish).
3. Patients with hematologic disorders or malignancies starting on any of the following monoclonal antibodies alone or in combination with chemotherapy (Blinatumomab, Daratumumab, Elotuzumab, Gemtuzumab, Obinutuzumab, and Rituximab).
4. Able to tolerate leukotriene antagonist including Montelukast.
5. Able to tolerate oral intake.
6. Available for follow up by phone and on site.

### *Exclusion Criteria*

1. Patients undergoing treatment with above monoclonal antibodies for indications other than stated in above eligibility criteria.
2. Patients who cannot provide informed consent in English or Spanish.
3. Patients taking Montelukast or other leukotriene antagonists for other indications at the time of screening.
4. Known allergic reactions to Montelukast or other leukotriene inhibitors.
5. On monoclonal antibodies other than the ones being studied (Blinatumomab, Daratumumab, Elotuzumab, Gemtuzumab, Obinutuzumab, and Rituximab).
6. History of uncontrolled depression or suicidal ideation or psychiatric illness.

7. Known Severe Hepatic Impairment (AST>10x ULN; ALT>10x ULN; ALP>10x ULN; and/or Bilirubin >5x ULN).
8. Patient with eosinophilic vasculitis.
9. Unable to comply with phone or in person follow-up.
10. Patients participating in another clinical trial.
11. Patients who are pregnant

## **Study Methods:**

### *Study design:*

This is a Phase II single arm open label study evaluating 10 mg Montelukast given at least 1 hour prior to infusion of monoclonal antibody in addition to standard premedication. Monoclonal antibodies being evaluated include those commonly used to treat hematologic and oncologic malignancies like (Blinatumomab, Daratumumab, Elotuzumab, Gemtuzumab, Obinutuzumab, and Rituximab).

The study will be introduced to patients who are undergoing treatment with above monoclonal antibody by principal investigator or sub-investigator during routine pre-initiation of immunotherapy or chemoimmunotherapy visits. Patients who are interested in hearing more about the study will be consented to participate in the study. Subjects will then be screened by study coordinator with the PI or Sub-I and those who meet inclusion/exclusion criteria will proceed on the study.

Drug for the study will be dispensed by one of the Research pharmacists affiliated to CCI during routine pretreatment evaluation for patient to take home. The study drug (Montelukast) will be purchased from commercial sources using the funds from the study sponsor. This is an investigator-initiated research with full funding from institutional pilot research grant from the Central California Faculty Medical Group (CCFMG). No additional internal or external funding will be utilized for this study.

Study subjects will be given 10 mg of Montelukast to be orally self-administered at least 1 hour prior to beginning of chemotherapy section. The administration of drug by patient will be verified and documented by inpatient or AIC nurse by history.

If the monoclonal antibody is given more than 3 times weekly, then patient will take Montelukast daily, including at least 1 hour prior to infusion or change of bag.

Standard premedication will be administered according to institution protocol. For details, see the flow chart below in appendix 1.

Rates, ratios and proportions with confidence intervals will be calculated for demographic characteristic and incidence of infusion reactions. McNemar's test will be used to test the differences of average incidence of infusion reaction between first and subsequent infusions.

*Intervention:*

Administration of Montelukast 10 mg at least 1 hour prior to initiation of up to 6 infusion doses/bag changes

*Control:*

Historic literature and retrospective chart review of patient's treated with above therapeutic monoclonal antibodies from January 2014 to December 2019.

*Covariates:*

History hypersensitivity medications, history of Asthma or Atopy, history of CAD/COPD, Other chemotherapy received by patient during the infusion and tumor burden.

*Study Implementation:*

This study is completely voluntary, and enrolment will not affect the treating oncologist's decision or treatment plan. The study medication, Montelukast, is an FDA approved drug for other indications and is not known to pose serious risk to cancer patient undergoing monoclonal antibody or cancer chemotherapy. Patients will be monitored closely for potential drug-drug interactions during the study period.

Information obtained from patients during the study period will be used solely for study purposes. No additional tissues or samples will be obtained for study purpose other than what is collected or required by treating physician as part of standard of care.

Privacy and confidentiality of patients' information will be protected per CMC guidelines.

Participation of study by subject is voluntary and will not require additional visits other than 24-hour post infusion phone call to complete a study related questionnaire. Study subjects will not be reimbursed for participation.

Study will be conducted over 2 years with an estimated yearly accrual of at least 40 patients per year.

The study will be conducted upon approval of CMC Institutional Review Board IRB and will follow Helsinki declaration and Good Clinical Guideline.

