The incidence rates of SIRs are highly variable ranging from 50-80% in Rituximab and Alemtuzumab to 20-30% in Trastuzumab and Cetuximab (4, 5). Incidence is highest with the first and probably the second doses but may recur with subsequent doses in up to 30%(6).

The severities of SIRs are also variable, ranging from mild involvement of single organ to severe reaction resulting in emergency room visit or hospitalization and death. In majority of patients with mild to moderate reactions, re-initiation of therapy with hours to days of break is possible.

Due to unpredictability of SIRs, efforts have been focused on decreasing the incidence and severity of infusion reaction with premedication. Most institutions have adopted various combinations of corticosteroid, acetaminophen and antihistamine as part of their premedication protocols with variable success in reducing the incidence and severity of SIRs.

Despite the above, SIRs still occur with high rates and severities resulting in treatment delays, infusion prolongations, need for additional doses of premedication, emergency room visits and

sometimes hospitalizations. These not only lead to increased cost of treatment but also lasting psychological impact of treatment of patients.

To mitigate the above, efforts are being directed at modifications of premedication or addition of newer agents to further reduce the incidence and severity of SIRs and hence improve tolerability.

Most recently, Montelukast, a mast cell stabilizer has been reported in multiple retrospective and observational studies to either decrease the incidence rate of infusion reactions, shorten infusion time and or decrease the use of additional doses of premedication like corticosteroids whose effect may be counterproductive (7). This has resulted in wide spread use of Montelukast as part of premedication of some monoclonal antibodies without formal study.

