Our pilot study seeks to evaluate whether 10 mg of Montelukast, when given at least one hour prior to infusion of monoclonal antibodies with high risk of infusion reaction (Blinatumomab, Daratumumab, Elotuzumab, Gemtuzumab, Obinutuzumab, and Rituximab) will decrease the incidence and severity of infusion reactions, shorten infusion time and improve tolerability. It also seeks to evaluate the frequency of use of extra doses of premedication during the infusion, particularly, corticosteroid whose use is associated with toxicity and is counterproductive to treatment in some situation. This will help identify new regimens to reduce the incidence and severity of SIRs. Information obtained will be hypothesis generating for a future Phase 3 randomized trial with eventual goal of modification of standard of care of monoclonal antibody premedication.

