**Data Collection:**

Demographic and clinical data will be collected according to the study plan (Appendix 2). Infusions will be administered per standard of care. The study investigators will obtain information about time of onset, time of completion, types and degree of infusion reaction(s), number of doses of additional medication used to treat infusion reaction and post infusion disposition locations. National Cancer Institute Common Terminology of Standard Adverse Effect (NCI CTCAE v5.0) will be used to grade Infusion-related reactions and Immune system disorder as shown in appendix 4.

Follow up phone calls to patients by study coordinator to ascertain additional reactions and treatments received will be documented. Patients will complete the study on completing 6th dose/bag change of infusion or progression of disease or change of therapy, whichever comes first. For patients on continuous infusion, change of bag will be used as reference point.

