**Statistical Analysis:**

Ratios and proportions with confidence intervals will be used to estimate the incidence and grades of infusion reactions. Proportions will also be used to report the use of additional medication during and after monoclonal antibody infusions. McNemar's test will be used to compare the incidence of infusion reaction between first and subsequent infusion.

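### McNemar's test is planned on an average over zero to five later infusions, which is not one yes/no value per patient, and neither section that names the test fixes the pair

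*Combined protocol and SAP*

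**What the plan says.** The test appears twice. Study design (under Study Methods) says that McNemar's "test will be used to test the differences of average incidence of infusion reaction between first and subsequent infusions". The Statistical Analysis section says that McNemar's "test will be used to compare the incidence of infusion reaction between first and subsequent infusion". The second version has no average, and its later infusion is singular and not numbered.

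The number of infusions varies by patient. The intervention is given "at least 1 hour prior to initiation of up to 6 infusion doses/bag changes". Data Collection adds: "Patients will complete the study on completing 6th dose/bag change of infusion or progression of disease or change of therapy, whichever comes first". A patient therefore has one first infusion and anywhere from none to five later ones. The same section says: "For patients on continuous infusion, change of bag will be used as reference point".

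On the expected time course, Background/Significance says: "Incidence is highest with the first and probably the second doses but may recur with subsequent doses in up to 30" per cent. It also describes the role of the study: "Information obtained will be hypothesis generating for a future Phase 3 randomized trial".

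No section gives a significance level for the test, or says how several later infusions become one value per patient.

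**The concern.** McNemar's test compares two yes/no values from the same patient. An average over k later infusions takes the values 0, 1/k, ..., 1. It is not binary when k exceeds 1 and is undefined when k is 0. The quantity in Study design therefore does not fit the test, and the Statistical Analysis wording does not settle which pair is meant.

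Once one pair is fixed, the test is valid. But the plausible pairs answer different questions:

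- **First infusion against any later reaction** sets one exposure against up to five. It can show more reactions later while the risk per infusion is flat or falling, and a reader would take that as worsening.
- **First against second infusion** is a fair one-to-one pair, but it uses two of up to six infusions. The plan itself expects the second dose to carry high risk too, so this pair can miss a fall that comes later.

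If the pair is left open, it can be chosen after the data are seen.

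**Working it through.** **Inputs from the plan.** 80 patients (Sample Size); at most six infusions, so at most five later ones (Study design); earlier end of follow-up possible (Data Collection). The plan states no power or alpha for this test, so there is no figure to reproduce.

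**Assumed, not in the documents.** Reaction rates; number of later infusions (five, three or two for everyone, or a uniform mix of 0 to 5); a logit random intercept per patient with SD 1 or SD 2, calibrated to the stated marginal rates; two-sided alpha 0.05.

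**Step 1: why the any-later pairing inflates.** With independent infusions at risk p, P(any reaction in k) = 1 − (1 − p)^k. At p = 15%:

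- k = 1: 15%
- k = 2: 1 − 0.85² = 27.8%
- k = 3: 1 − 0.85³ = 38.6%
- k = 5: 1 − 0.85⁵ = 55.6%

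Within-patient correlation lowers the last figure to 48% (SD 1) or 38% (SD 2). Both are still far above 15%.

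**Step 2: simulation.** 6,000 trials per scenario. The exact McNemar p-value is 2·P(Bin(b + c, ½) ≤ min(b, c)), capped at 1, where b and c are the two discordant counts. The comparator is a logistic GEE with a first-versus-later factor, independence working correlation, patient-clustered robust errors with an n/(n − 1) correction, and each patient's later infusions weighted by 1/(number given). Entries are % of trials, SD 1 / SD 2.

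| Scenario and result | Five later | Three later | Two later | 0–5 mix |
|---|---|---|---|---|
| Flat 15%: any-later shows an increase | 99.9 / 98 | 86 / 74 | 38 / 31 | 69 / 52 |
| 25% to 15%: any-later shows an increase | 89 / 56 | 26 / 10 | 2 / 1 | 16 / 5 |
| 25% to 15%: first vs second finds the fall | 31 / 40 | 31 / 40 | 31 / 40 | 26 / 33 |
| 25% to 15%: GEE finds the fall | 63 / 74 | 59 / 68 | 53 / 63 | 50 / 58 |
| 50% to 30%: any-later shows an increase | 89 / 35 | 20 / 2 | at most 1 | 6 / 1 |
| 30%, 25%, then 15%: GEE finds the fall | 79 / 89 | 65 / 77 | 45 / 57 | 47 / 55 |

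At a flat 15%, first versus second rejects in about 3% of trials in total and GEE in about 5%. In the 30%, 25%, then 15% scenario, first versus second finds a decline in only 7% to 10%. In the mix, 80/6 ≈ 13 patients have no later infusion and so no pair.

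**Step 3: where the problem disappears.** For a fall from 50% to 15%, any-later shows an increase in at most 1% of trials, and both GEE and first versus second find the fall in over 99%. For 50% to 30% with complete pairs, first versus second finds the fall in about 76% / 86%.

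**Step 4: a different correlation model.** With independent infusions, five later ones and a flat 25%, any-later (76.3%) declares later infusions worse in about 100% of trials. A reaction at the majority of later infusions declares them better in 60%. Second infusion rejects in 3.2%. At 50% then 30%, any-later says worse in about 99%, majority says better in about 99.5% and second infusion says better in about 68%. With within-patient correlation 0.3 and flat risks of 10% to 40%, any-later still rejects in 92% to 100%.

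**The case against.** The strongest reply is that the worst figures come from a pairing the plan does not state. Neither section speaks of any or at least one later reaction, and the singular in Statistical Analysis could mean first versus second infusion, for which the test is sound. This stands in part: reversal needs the any-later pairing, several later infusions and a modest fall. But the plan does not number the infusion, Study design uses the plural, and a dichotomised average is not neutral either. The majority rule shows a false decline in 60% of trials at a flat 25% under independence, and in about 11% with correlation 0.3.

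The average might also be loose wording for a group proportion. Even so, the patient-level pair is undefined.

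The remaining points are fair:

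- The contrast serves no listed objective or endpoint, and the primary endpoint is estimation of incidence. That limits the harm to this contrast, although it is the only hypothesis test the plan names.
- Bag changes are already counted alongside doses ("up to 6 infusion doses/bag changes"), so their treatment here needs only a clarifying sentence. The study plan in Appendix 2 is not in the text reviewed and may say more.
- Losing patients with no second value is a feature of any paired test, not a fault of this one.
- GEE is not free of bias, as set out under the change below.

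**Conclusion.** The concern holds. The test named in Study design does not fit the quantity it is applied to, and Statistical Analysis does not supply the missing pair. Depending on an unstated choice, the same process can give opposite conclusions. With five later infusions and a true fall from 25% to 15%, any-later reports an increase in 89% / 56% of trials, while the other two analyses point to a fall. Even the valid first-versus-second pair has about half the power of the GEE in that case, and far less if the second dose also carries high risk.

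These sizes rest on assumed rates, infusion counts and between-patient spread. The mismatch between test and quantity does not. It should be corrected before analysis. It does not threaten the primary estimate.

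**What to change.** In Study design and Statistical Analysis, replace McNemar's test with one prespecified analysis in identical words: a logistic GEE of reaction (yes/no) per infusion, robust errors clustered on patient, first versus later as the factor, all infusions included. Weight each patient's later infusions by 1/(number given), so that the later rate is the patient-level average that Study design names. Also:

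- Report the reaction proportion with a 95% confidence interval for infusion 1, infusion 2 and infusions 3 to 6, the last clustered on patient. Expected precision: 20/80 gives a Wilson interval of 16.8% to 35.5%, and 12/80 gives 8.8% to 24.4%. At 15%, infusions 3 to 6 have a half-width of 4.5 / 5.5 points (SD 1 / SD 2), against 3.9 if clustering is ignored.
- State whether each bag change counts as a separate later infusion, and report how many patients have no later infusion and why.

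If McNemar's test is kept, name the same single pair in both sections, for example first versus second infusion, and accept the lower power shown above. Adjustment for antibody and a mixed-model sensitivity analysis are optional.

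**Cost.** Wording and one standard model, slightly more complex than a 2×2 test, on data already collected. The weights matter. Suppose half the patients have 25% risk and one later infusion, and half have 10% risk and five. The first-infusion rate is (25% + 10%)/2 = 17.5% and the pooled later rate is (1 × 25% + 5 × 10%)/6 = 12.5%, with no change in any patient. Unweighted GEE reports a decline in 21% of trials, weighted GEE in 3%. Weighting costs about 1 to 4 points of power in the 0–5 mix (54% / 59% unweighted, 50% / 58% weighted, for 25% to 15%).

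Neither method removes drop-out bias. With no true change, five later infusions and an assumed 30% of first-infusion reactors stopping, GEE shows a false decline in about 4% / 7% of trials (5% / 9% at a 30% reaction rate), against a nominal 2.5%. First versus second shows a false increase in about 6% / 5% (9% / 8%). The Synopsis and Background/Significance say most patients can restart, so the actual loss may be smaller.

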## Synopsis

The use of monoclonal antibodies either alone or as part of chemoimmunotherapy in oncology, benign and malignant hematology is expanding. Each year, United States Food and Drug administration (FDA) approves new agents or expands the indications of already approved agents. Of the 17 therapeutic monoclonal antibodies approved in 2017, 50% of them are indicated for hematologic and oncologic condition. With increasing number of approved agents and expansion of indications of existing agents, therapeutic monoclonal antibodies have become one of the fastest growing areas in the management of benign and malignant hematologic condition. With advancement of recombinant technology, newer agents are either partially or fully humanized. Despite this, they still carry significant risk of immune and non-immune mediated adverse events. Most of the therapeutic monoclonal antibody related adverse events (MCAAE) are either anaphylaxis or standard infusion reactions.

The severity of reaction is variable, ranging from mild involvement of single organ to severe and life-threatening reactions requiring hospitalization or even resulting in death. In a majority of patients, re-initiation of infusion following resolution of symptoms with or without additional medical intervention is possible.

Even for mild infusion reactions, where re-initiation of infusion is possible, there is resultant delay in delivery of infusions, distress to patients, and additional utilization of health care resources.

Due to unpredictability of standard infusion reaction, efforts have been focused on premedication to decreasing the incidence and severity of infusion reaction. Most institutions have protocols using corticosteroid, acetaminophen and antihistamine as part of their premedication protocols. This has reduced but not eliminated standard infusion reactions. Most recently, mast cell stabilizers are being added to standard protocols to further reduce the incidence and severity of standard infusion reactions with variable anecdotal success without formal study. Of all the monoclonal antibodies, only Daratumumab has been evaluated using this strategy.

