## **Design of the Study:**

This is a Phase II, single arm, open label, clinical trial.

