## **Sample Size:**

A total of 100 patients will be screened with anticipated enrollment of 80 into the study. This is based on resources and estimated patients' availability for the study.

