## **Patient Population (Eligibility and Exclusion Criteria):**

Consecutive patients who are seen and treated for various hematologic or oncologic malignancies with monoclonal antibodies (Blinatumomab, Daratumumab, Elotuzumab, Gemtuzumab, Obinutuzumab, and Rituximab) in Community Medical Centers- CMC (Community Regional Medical Center (CRMC), and Clovis Community Medical Center (CCMC)) and affiliated Ambulatory Infusion Centers (East Medical Plaza AIC, Clovis Community AIC, and Community Cancer Institute AIC) will be approached for study enrollment. Patients will be recruited from CCI, CCMC, and CRMC when they present for evaluation for hematologic or oncologic malignancy by PI or one of the sub-I's. Only patients treated by PI or sub-I's will be recruited into the study. No additional patients from external referral from other hematologist, oncologist, or PCP will be recruited unless they are seen by PI or Sub-I's for treatment evaluation.

Potential subjects will be approached when they present for pre-chemotherapy evaluation for their first dose of chemoimmunotherapy or immunotherapy for above named therapeutic monoclonal antibodies. Subjects who express interest in the study will then be consented for screening, registration and enrollment.

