### **Confidentiality and Privacy:**

Currently all data for patients who will be starting a treatment regimen that includes monoclonal antibodies either alone or in combination with chemotherapy are kept confidential. Study information for retrospective study will be obtain from EPIC EMR. All information obtained will be confidential and only need to know information will be obtain from EPIC for study purposes only. Both retrospective and prospective information will be stored on password protected, secured online REDCAP database.

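### The local historical control is one closed 2014-2019 block with no account of calendar period or antibody, so a change in practice or antibody mix cannot be separated from a Montelukast effect

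*Combined protocol and SAP*

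**What the plan says.** All references are to the combined protocol and SAP.

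- **Design of the Study:** "This is a Phase II, single arm, open label, clinical trial".
- **Hypothesis:** adding Montelukast is expected to cut the incidence of standard infusion reactions (SIRs) by at least 50% relative to historic data.
- **Study Methods, Control:** historic literature and a "retrospective chart review of patient's treated with above therapeutic monoclonal antibodies from January 2014 to December 2019". The Confidentiality and Privacy section gives the source: "Study information for retrospective study will be obtain from EPIC EMR".
- **Study Methods, Covariates:** hypersensitivity history, asthma or atopy, CAD/COPD, other chemotherapy and tumour burden. Neither antibody nor calendar year is listed, and no model uses the list.
- **Statistical Analysis:** proportions with confidence intervals, and a McNemar test of first against later infusions within the cohort. There is no analysis against the control.
- **Evidence of change:** the Synopsis says that each year the FDA "approves new agents or expands the indications of already approved agents". Background/Significance says that reaction risk varies with agent, indication and patient characteristics, that premedication is being modified, and that Montelukast is already widely used with some antibodies.
- **Size and timing:** "A total of 100 patients will be screened with anticipated enrollment of 80 into the study"; "Study will be conducted over 2 years with an estimated yearly accrual of at least 40 patients per year". No enrolment start date is given.

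**The concern.** In a single-arm trial, the meaning of a decrease rests on the comparator. Here the comparator is six years of charts treated as one block, covering six antibodies with different reaction risks. If the antibody mix, the indications, the premedication or the charting of reactions differed between those years and the trial, the crude SIR rate would differ even if Montelukast did nothing. The plan has no step that would reveal this, although the chart review could show both a trend within 2014-2019 and the antibody mix. A second contaminant is Montelukast itself: nothing excludes control patients who received it, and their presence would dilute the contrast.

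Background/Significance says the results are to generate hypotheses for a randomised Phase 3 trial. A decrease produced by drift would misinform that trial, and a real effect masked by drift might stop it.

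**Working it through.** **1. The plan's own figure.** 2 years × 40 per year = 80, which agrees with the stated enrolment. The Sample Size section adds: "This is based on resources and estimated patients' availability for the study". No alpha, power, control rate or control size is stated, so 80 cannot be checked against a power formula.

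**2. Criterion.** The only success criterion in the protocol is the halving in the Hypothesis section. With n = 80 and one yes/no outcome per patient, an observed halving means:
- at most 80 × 0.25 = 20 patients with an SIR for a 50% benchmark;
- at most 80 × 0.15 = 12 for a 30% benchmark.

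**3. Benchmarks (assumed).** The protocol gives no pooled rate for its six antibodies. Background/Significance quotes 50-80% for rituximab and alemtuzumab and 20-30% for trastuzumab and cetuximab; of these four, only rituximab is a study drug. I take 50% and 30% as the range and treat each as fixed.

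**4. Drift (assumed).** The midpoint of January 2014 to December 2019 is the end of 2016. If the trial ran in 2020-2021, its midpoint would be the end of 2020, 4 years later. A drift of 1 to 4 points per year then gives 4 to 16 points. The documents support neither the dates nor the rate, so these figures show sensitivity only.

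**5. False halving, no drug effect, background falling by d.** P(X ≤ 20) with X ~ Binomial(80, 0.50 − d), and P(X ≤ 12) with X ~ Binomial(80, 0.30 − d):

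| Fall d (points) | 50% benchmark: true rate | P(observed halving) | 30% benchmark: true rate | P(observed halving) |
|---|---|---|---|---|
| 4 | 46% | 0.01% | 26% | 1.4% |
| 8 | 42% | 0.1% | 22% | 8.0% |
| 12 | 38% | 1.0% | 18% | 30% |
| 16 | 34% | 5.4% | 14% | 67% |

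At the 30% benchmark a 16-point fall is itself more than a halving (14% against 15%), which explains the last entry.

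**6. Hidden effect, drug truly halves the rate, background rising by d.** The true trial rate is (benchmark + d)/2. Without drift an observed halving has probability 56% (50% benchmark) or 58% (30%). With a rise of 8 points the true rates are 29% and 19%, and the probabilities fall to 26% and 22%.

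**7. Antibody mix alone.** Assume SIR rates of 65% for higher-risk and 25% for lower-risk agents (the midpoints of the two quoted ranges). If the higher-risk share is 80% among controls and 50% in the trial:
- controls: 0.80 × 65% + 0.20 × 25% = 57%;
- trial: 0.50 × 65% + 0.50 × 25% = 45%.

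The apparent relative reduction is 1 − 45/57 = 21%, with no change within any agent. Stratifying by antibody removes this component.

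**The case against.** The strongest reply is that this is a hypothesis-generating pilot. The primary objective and endpoint only report or estimate SIR incidence, the Statistical Analysis section plans no test against the control, and some case-mix covariates are named. Reliance on historical data is inherent in a single-arm design. This stands as far as it goes: the bias enters through the comparison in the Hypothesis section, not through a planned test. It does not remove the point, because that comparison will be made informally if it is not made properly.

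Four stronger readings are tempting, and the documents do not support them.

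- **That every change in practice or case mix is counted as drug effect.** This presumes a formal trial-versus-control analysis, and none is planned. What can be said is that such changes cannot be separated from a drug effect.
- **That the control certainly shares no calendar time with the trial.** This is a reasonable inference from a closed retrospective window, but no enrolment dates are given. The Synopsis remark on new agents is also limited evidence, since the control is restricted to the six named antibodies; changed indications, mix or premedication remain relevant. No passage shows a changing SIR rate.
- **That modest drift very probably gives a false positive.** If success meant an exact 95% upper limit below the benchmark, drifts of 4 to 16 points would give 7.8% to 78% at 50% and 8.5% to 91% at 30%. That rule is not in the protocol.
- **That a concurrent untreated cohort is being wasted.** Recruitment is restricted ("Only patients treated by PI or sub-I's will be recruited into the study"), so non-enrolled patients may exist. But their number is unknown, they are selected by physician or refusal, some may receive Montelukast, and charts would lack the trial's 24-hour call and prospective grading. Study Methods also rules out further funding.

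**Conclusion.** The concern holds in a limited form. The protocol poses a comparison with historic data, fixes the local control as one closed block, and handles neither calendar period nor antibody, so an observed decrease cannot be attributed to Montelukast as distinct from a period or mix change.

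Under the protocol's own halving criterion, the risk of a false halving is small at a 50% benchmark (at most 5.4% for drifts up to 16 points). It is substantial at 30% once drift reaches 12 points or more (30% to 67%). These figures assume 80 patients, one binary outcome each, a benchmark without sampling error, and drift sizes that the documents do not supply. The direction of bias is not fixed: prospective grading and the follow-up call could raise detected SIRs relative to charts, and Montelukast use among controls would shrink the contrast.

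The change is worth making because it is cheap. The point does not show that the trial's result would be wrong.

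**What to change.** Amend the Control and Covariates paragraphs of Study Methods and the Statistical Analysis section as follows.

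1. Tabulate chart-review SIR incidence by antibody and by calendar period, grouping years where cells are small (six agents by six years is up to 36 cells). Record Montelukast exposure for each control patient, and state the trial's enrolment dates.
2. Make the Hypothesis comparison stratified or standardised by antibody. Repeat it as a sensitivity analysis using only 2018-2019 controls, and again without Montelukast-exposed controls.
3. State in advance that if control incidence trends over 2014-2019, or if a restricted comparison differs materially from the main one, the report will say that the decrease cannot be attributed to Montelukast alone. Define what counts as material before the data are seen.

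A regression term for calendar year is not recommended. Without overlap between control and trial it separates drug from period only by extrapolating the earlier trend.

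Extending the chart review to non-enrolled concurrent patients is optional, if resources allow, and then only as a descriptive sensitivity comparison.

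**Cost.** Items 1 to 3 need one more abstracted field and extra tabulation of charts already to be reviewed; no patients are added. The price is precision: two of six years is about a third of the controls if volume was even, so the control's standard error grows by about √3 ≈ 1.7. The optional extension would need about two more years of abstraction and an IRB modification.
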